5.6 Criteria for Removal from Study

Patients will be removed from study when any of the criteria listed in [Section 5.4](#) applies. The reason for study removal and the date the patient was removed must be documented in the case report form. The patient should be followed per protocol requirements.

AEs will be described and coded based upon the National Cancer Institute Common Terminology Criteria for Adverse Events v4.0 (NCI CTCAE v4.0). Safety will be evaluated by assessing and chronicling treatment-related AEs.

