Cohort	INCB024360 Dosing	MELITAC 12.1 Dosing	Blood draws	Tumor biopsies including FNA
A Pts.enrolled >6 wks after failing anti- PD-1/PDL-1	300 mg po bid continuous for 98 days (3 months)	Intradermal/subcutaneous Days 21, 28, 35, 56, 77, 98 (Weeks 3, 4, 5, 8, 11, and 14)	Pretreatment day 0 and on days 21, 42, 98, and 112	Days 0, 21, 42, and (optional day 112) and (optional when coming off study including for progression)
B Pts.enrolled 2-6 wks after failing anti- PD-1/PDL-1	100 mg po bid continuous for 98 days (3 months)	Intradermal/subcutaneous Days 21, 28, 35, 56, 77, 98 (Weeks 3, 4, 5, 8, 11, and 14)	Pretreatment day 0 and on days 21, 42, 98, and 112	Days 0, 21, 42, and (optional day 112) and (optional when coming off study including for progression)

Abbreviations: bid, twice per day; FNA, fine-needle aspiration; po, orally; pre-tx, pretreatment; SC, subcutaneous

Enrollment will be staggered so that only 3 patients will initially be treated at the 300-mg bid dose in order to observe their response to the INCB024360-MELITAC 12.1 combination. After the first patient is started on INCB024360, treatment will proceed for 2 weeks before the second patient is started on INCB024360 monotherapy. Before the second patient starts the combination of INCB024360 and MELITAC 12, the first patient will have already received the second vaccination of MELITAC 12.1 in combination with INCB024360 and observed for any toxicity. The third patient will start INCB024360 monotherapy 2 weeks after patient number 2 has received the combination of INCB024360 and MELITAC 12.1 and been observed for toxicities. After the first 3 patients are treated at the 300-mg bid dose of INCB024360 in combination with the MELITAC 12.1 and found to tolerate the combination well, the dose of INCB024360 will be 300 mg BID for subsequent patients. Those patients treated with anti-PD-1/PDL1 antibody who have failed therapy and enrolled in the study 6 weeks or longer after progression of disease will be enrolled in Cohort A and receive 300 mg BID of INCB024360. Patients who fail anti-PD-1/PDL-1 therapy and enroll within 2-6 weeks of progression of disease will receive 100 mg BID in Cohort B. All other patients enrolled in the study will receive INCB024360 300 mg BID.

A total of 12 patients will be enrolled in the study. Assignment to Cohort A or B is for dose assignment only.

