5.1.1 CTEP IND Agent(s): N/A

5.1.2 Other Agent(s): **INCB024360**

Combining INCB024360 with the multipeptide vaccine MELITAC 12.1 is a novel approach. Although no adverse findings in toxicology or safety pharmacology assessments have been described herein, and the most common grade 1 or 2 AEs at the recommended Phase-II dose (600 mg) include fatigue, nausea and vomiting, constipation, and anorexia; to decrease the possibility of unanticipated toxicities with the combination, the dose of INCB024360 in the first 3 patients treated in the study will be at the dose of 300 mg bid.

Weak cross-reactivity of INCB024360 to the human vasopressin 1a receptor, dopamine receptor, and carbonic anhydrase II may lead to changes in blood pressure or blood electrolytes. In 28-day toxicology studies, C_{max} values have exceeded the IC_{50} for the IDO1 enzyme (72 nM) by up to 37-fold and the IC_{50} for the vasopressin 1a receptor by up to 4-fold (13-fold in single-dose studies) in the absence of any toxicity, so the risk of unintended pharmacological activity is expected to be low.

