5.1.4 Other Modalities or Procedures: N/A

5.1.5 Investigational Imaging Agent Administration: N/A

5.2 **Definition of Dose-Limiting Toxicity:**

Dose-limiting toxicities (DLTs) include all Grade 3 AEs regardless of investigator attribution or relatedness except for those listed below.

Based on investigator determination the following Grade 3 toxicities can be deemed non-DLT:

- adverse event with a clear alternative explanation (e.g. due to disease progression)
- transient toxicities (≤ 72 hours)
- injection site reactions that are expected and do not require any surgical intervention or repair
- abnormal laboratory values without associated clinically significant signs or symptoms

There are two exceptions to the above. Grade 1 or greater ocular toxicities will be considered a DLT. Grade 2 LFT elevations will be considered a DLT.

In the event of a DLT, it will be determined by the safety team whether both the INCB024360 AND the MELITAC 12.1 will be permanently discontinued. In cases of vaccine injection site reaction or other vaccine related adverse events the INCB024360 may be continued if the vaccine related adverse event continues to show improvement. Management and dose modifications associated with the above adverse events are further outlined in [Section 6](#).

5.3 **General Concomitant Medication and Supportive Care Guidelines**

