Peripheral sensory neuropathy	Peripheral sensory neuropathy (Gr 2)
PSYCHIATRIC DISORDERS	
Insomnia	
RESPIRATORY, THORACIC AND MEDIASTINAL DISORDERS	
Cough	Cough (Gr 1)
Dyspnea	Dyspnea (Gr 1)
Hypoxia	
SKIN AND SUBCUTANEOUS TISSUE DISORDERS	
Rash maculo-papular	Rash maculo-papular (GR 2)

¹This table will be updated as the toxicity profile of the agent is revised. Updates will be distributed to all Principal Investigators at the time of revision. The current version can be obtained by contacting [contact]. Your name, the name of the investigator, the protocol and the agent should be included in the e-mail.

²INCB024360 can result in severe and potentially fatal immune-mediated adverse events. These include (but are not limited to) autoimmune hepatitis and autoimmune hypophysitis.

Adverse events reported on INCB024360 trials, but for which there is insufficient evidence to suggest that there was a reasonable possibility that INCB024360 caused the adverse event:

Investigations – GGT increased

Metabolism and nutrition disorders – Hypernatremia
Respiratory, thoracic and mediastinal disorders – Pneumonitis
Vascular disorders - Hypertension

Note: INCB024360 in combination with other agents could cause an exacerbation of any adverse event currently known to be caused by the other agent, or the combination may result in events never previously associated with either agent.

No AEs have been reported consistent with the serotonin syndrome.

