7.3.4 Additional Protocol-Specific Expedited Adverse Event Reporting Exclusions: N/A

7.4 Routine Adverse Event Reporting

All Adverse Events **must** be reported in routine study data submissions. **AEs reported through CTEP-AERS must also be reported in routine study data submissions.**

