12.3 Collaborative Agreements Language – N/A

13. STATISTICAL CONSIDERATIONS

13.1 Study Design/Endpoints

The proposed study is a Phase II, open label, multicenter study of the administration of INCB024360, an IDO1 inhibitor, plus a multipeptide melanoma vaccine, MELITAC 12.1, in patients with advanced (i.e., surgically incurable stage III or IV) melanoma having tissue amenable to serial biopsy.

The first 3 patients will be administered the INCB024360 in a reduced amount of 300 mg bid and enrolled in a staggered design with a 2-week waiting period between each of the first 3 patients ([Table 5.1](#)). This is a safety precaution due to unknown effects of the combination of INCB024360 with the multipeptide melanoma vaccine. Although both agents have excellent safety profiles, unexpected toxicities could occur when used together.

Each patient's tumor(s) will be biopsied before therapy and during therapy to assess the effects of INCB024360 and vaccine by IHC and transcriptome analysis ([Table 5.1](#)).

INCB024360 is expected to normalize serum Kyn/Trp ratios, in turn altering the tumor microenvironment, which includes the number and character of tumor-infiltrating T cells. The addition of MELITAC 12.1, a multipeptide melanoma vaccine, will be used to compare INCB024360 alone and with the vaccine. Effects of IDO inhibition on systemic vaccine-induced immunity will be assessed by evaluating peripheral blood immune responses to the MELITAC 12.1 vaccine. The comparator for immune responses will be taken from published experience with similar patients treated with the same vaccine regimen but without INCB024360 [[[name] 2011](#); [[name] 2009](#)].

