13.3 Sample Size/Accrual Rate

The study plans to enroll a total of 12 patients at 3 or 4 clinical research sites. Each patient will act as their own control. Patients without adequate sampling for immune responses will be replaced.

Accrual rate of patients is expected to be approximately 3 patients per month.

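### Section 5.6 evaluates safety from treatment-related AEs, so the Objective 6 summary depends on open-label attribution and does not match the DLT definition

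*Combined protocol and SAP*

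**What the plan says.** The sentence that names the AE set is at the end of section 5.6: "Safety will be evaluated by assessing and chronicling treatment-related AEs". Objective 6 (section 1.2) is safety and tolerability. Section 13.5.4 repeats that objective and adds no summary, table or estimate. Section 13.6.1 says who is evaluable for toxicity, and section 11 names CTCAE v4.0 as the grading system. None of these says which events will be summarized.

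Other sections are not filtered by relatedness:

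- Section 5.2: DLTs "include all Grade 3 AEs regardless of investigator attribution or relatedness except for those listed below". Section 6 repeats this in substance.
- Section 5.1: the study stops on two DLTs in the first 6 patients at 300 mg, with no relatedness condition.
- Section 7.4: all AEs must "be reported in routine study data submissions".
- Section 7.3.3: serious AEs are reported whether or not they are thought related.

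Section 6 does apply a filter. The regimen counts as safe while no more than 33% of participants have a treatment-related DLT. Accrual closes above that level, except that 1 in the first 3 patients is acceptable.

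On design, section 13.1 says "The proposed study is a Phase II, open label, multicenter study", section 13.3 says "Each patient will act as their own control", and section 5.1 says "A total of 12 patients will be enrolled in the study".

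**The concern.** Attribution is a weak filter in this design. The investigator knows what the patient received, and no concurrent group shows how often an event occurs without treatment. The published comparator in section 13.1 is for immune responses, not for toxicity. Section 5.1.2 says "Combining INCB024360 with the multipeptide vaccine MELITAC 12.1 is a novel approach", and section 7.1.2 warns that "the combination may result in events never previously associated with either agent". An event with no precedent for either agent is hard to attribute in either direction.

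A statistician following section 5.6 as written would tabulate the related events and leave out those judged unrelated, although they are in the database. The resulting table need not agree with the DLT count. A Grade 3 event judged unrelated can be a DLT under section 5.2, yet be absent from the section 5.6 summary and from the 33% criterion in section 6.

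**Working it through.** The documents give no safety figure to reproduce: no target rate with a power or confidence statement, and no planned safety table. The check is a comparison of texts, followed by two pieces of arithmetic.

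**1. Where attribution counts**

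| Section | Use | Filtered by relatedness? |
|---|---|---|
| 5.6 | Safety evaluation | Yes |
| 6, 33% criterion | Regimen judged safe; accrual closed | Yes |
| 5.2 and 6, DLT definition | What counts as a DLT | No at the outset; the investigator may exclude a Grade 3 event with a clear alternative explanation |
| 5.1 | Two DLTs in the first 6 at 300 mg | No further condition |
| 7.3.3, 7.4 | Collection and reporting | No |
| 11 | CTCAE v4.0 grading | Not addressed |
| 13.5.4 | Statistical section | Not addressed |

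Ocular events show the same mismatch. Sections 5.2 and 6 make any ocular toxicity of Grade 1 or more a DLT. Section 5.5 and the footnote to the ocular table in section 6 refer to treatment-related Grade 1 events.

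**2. Effect of one re-attributed patient**

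With n = 12, one patient is 1/12 = 8.3 percentage points on any patient-level rate.

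**3. Sensitivity of the 33% criterion to attribution (illustration)**

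Read literally, 4/12 = 33.3% exceeds 33%, so 4 of 12 crosses the limit. This reading fits the stated exception, because 1/3 = 33.3% would otherwise cross it too. Let r be the all-cause DLT rate and f the share of those events attributed to treatment. Both are assumptions, not figures from the documents. With q = r × f, the chance that at least 4 of 12 count at full accrual is the sum over k = 4 to 12 of C(12,k) q^k (1−q)^(12−k). Two variants are shown: 33% taken as one third (at least 5 of 12), and the literal rule checked after every patient with the exception for the first 3.

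| r | f | q | At least 4 of 12 | At least 5 of 12 | Checked after each patient |
|---|---|---|---|---|---|
| 0.30 | 1.00 | 0.300 | 0.507 | 0.276 | 0.686 |
| 0.30 | 0.75 | 0.225 | 0.276 | 0.110 | 0.483 |
| 0.30 | 0.50 | 0.150 | 0.092 | 0.024 | 0.259 |
| 0.40 | 1.00 | 0.400 | 0.775 | 0.562 | 0.872 |
| 0.40 | 0.75 | 0.300 | 0.507 | 0.276 | 0.686 |
| 0.40 | 0.50 | 0.200 | 0.205 | 0.073 | 0.408 |

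At an assumed all-cause rate of 30%, attributing half the events rather than all of them lowers the chance of crossing the limit from 0.507 to 0.092. The same causality judgments feed the section 5.6 summary. The table itself describes the section 6 criterion, which a change to the AE tables would not alter.

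**The case against.** The strongest reply is that section 5.6 is one descriptive sentence in a section on removal from study. It does not say that unrelated events will be ignored. All AEs go into routine data, serious AEs are reported whatever their cause, and the early rule in section 5.1 carries no relatedness condition. All of this stands. No event is lost from the database or from expedited reporting; what is affected is the planned summary. The reply does not supply another AE set, because sections 11, 13.5.4 and 13.6.1 name none.

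Three stronger readings are tempting, and the documents do not support them.

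- *Safety rests on related events alone.* The text contains no such restriction, and sections 6 and 11 also address how safety is judged.
- *The DLT count ignores attribution.* It starts from all Grade 3 events. However, sections 5.2 and 6 let the investigator set aside an event with a clear alternative explanation, such as progression, and that is a causality judgment.
- *Grade 3 fatigue and dyspnea in the earlier vaccine data show how much would be dropped.* In Table 7.1.4.1, 15 of 51 patients had any Grade 3 event and 13 of 51 had a Grade 3 injection-site reaction. Removing every fatigue and dyspnea event therefore changes the any-Grade-3 patient rate by at most (15 − 13)/51 = 2/51 = 3.9 points. Section 7.1.2 also lists both terms as possibly related to INCB024360, so investigators may well attribute them. Section 5.1.3 describes the first 51 vaccinees as having received GM-CSF, whereas section 2.3.2 proposes peptide in IFA here after finding no benefit from adding GM-CSF.

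**Conclusion.** The point holds as a defect in the analysis text and as an inconsistency between sections. As written, the Objective 6 summary depends on unblinded attribution in 12 patients without a concurrent control, and it leaves out events that the trial already collects. The size that follows from the documents alone is 8.3 points per re-attributed patient. The probabilities for the 33% criterion show how far attribution can matter, but they rest on assumed rates and assumed attribution shares. They do not predict how investigators in this trial will judge events.

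The importance is moderate. Safety is a secondary objective, but this is a novel combination and the all-cause summary needs no new data.

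**What to change.** In sections 5.6 and 13.5.4, state that all AEs from the first INCB024360 dose will be tabulated by worst grade regardless of attribution, with treatment-related AEs shown as a subset. Use the toxicity population of section 13.6.1.

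Include the events collected at the 10- and 36-week post-treatment visits in the study calendar. A cut-off at 30 days after the last dose would drop them; events beyond 30 days can be shown separately. Optionally, show events before and after the first vaccine separately, which distinguishes INCB024360 alone from the combination.

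Separately, reconcile section 5.6 and the 33% criterion in section 6 with the DLT definition in sections 5.2 and 6, so that the protocol says once whether attribution counts. The ocular wording in sections 5.2, 5.5 and 6 belongs in the same reconciliation. Which rule should govern is for the sponsor to decide.

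The cost of the tabulation change is table shells. The reconciliation is a text amendment. Neither needs additional data.

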6. DOSING DELAYS/DOSE MODIFICATIONS

All toxicity associated with prior treatment must resolve to grade 1 or less off steroid treatment for at least 2 weeks. Patients who have discontinued treatment for pulmonary, renal or neurologic toxicity or who have experienced grade 4 toxicity should not be enrolled in the study.

All related toxicities will be reviewed by the protocol P.I., participating site P.I.s, CTEP and the CITN Coordinating Center for an indication to change the dosing schedule.

The selected doses of INCB024360 and MELITAC 12.1 have been established as having excellent safety profiles. Dose escalation is not planned or necessary. However, when used together, unexpected toxicities might occur. Thus, rules for stopping will be incorporated in the event that dose-limiting AEs are observed.

Toxicities for each agent will be monitored continuously and will be graded by the NCI CTCAE v4.0 with stopping rules for AEs. At the discretion of the investigators, treatment may be held for up to 14 days to permit the evaluation or resolution of symptoms that may be unrelated to treatment but may affect patient safety (e.g., influenza, minor trauma).

DLT's include all Grade 3 AEs regardless of investigator attribution or relatedness except for expected grade 3 injection site reactions. ([section 5.5](#))

Based on investigator determination the following Grade 3 toxicities can be deemed non-DLT:

- adverse event with a clear alternative explanation (e.g. due to disease progression)
- transient toxicities (≤ 72 hours)
- injection site reactions that are expected and do not require any surgical intervention or repair

- abnormal laboratory values without associated clinically significant signs or symptoms

There are two exceptions to the above: Grade 1 or greater ocular toxicities will be considered a DLT. Grade 2 LFT elevations will be considered a DLT.

In the event of a DLT, it will be determined by the safety team whether both the INCB024360 AND the MELITAC 12.1 will be permanently discontinued.

Vitiligo will not be considered a DLT.

Pages 33, 34 and 35 include tables for some of the more common AE's including instructions for handling. For any AE's not listed in these tables, proceed in the following manner:
Grade 1 and Grade 2: Continue to monitor, follow and grade these adverse events.
Grade 3: Stop Protocol Therapy including both INCB024360 and MELITAC 12.1
Grade 4: Stop Protocol Therapy including both INCB024360 and MELITAC 12.1

In addition, treatment will be discontinued for (a) Any DLT, (b) disease progression requiring other therapy, (c) noncompliance with study requirements, (d) other safety considerations in the judgment of the investigator, or (e) patient request.

The treatment regimen will be considered safe as long as the number of participants experiencing a treatment-related AE (DLT) does not exceed 33%. If more than 33% of patients accrued are known to have experienced a treatment-related DLT, the study will be closed to further accrual, except that 1 treatment related DLT observed out of the first 3 patients accrued will be acceptable and will not result in the closing of the study.

Nausea	Management/Next Dose for INCB024360	Management/Next Dose for MELITAC 12.1
≤ Grade 1	No change in dose	No change in dose
Grade 2	No change in dose	No change in dose
Grade 3	Off Protocol Therapy	Off Protocol Therapy
Grade 4	Off protocol therapy	Off protocol therapy
Recommended management: antiemetics		

Vomiting	Management/Next Dose for INCB024360	Management/Next Dose for MELITAC 12.1
≤ Grade 1	No change in dose	No change in dose
Grade 2	No change in dose	No change in dose
Grade 3	Off Protocol Therapy	Off Protocol Therapy
Grade 4	Off protocol therapy	Off protocol therapy
Recommended management: antiemetics		

Investigations (Liver Function Tests ALT + AST)	Management/Next Dose for INCB024360	Management/Next Dose for MELITAC 12.1
< Grade 1	No change in dose	No change in dose
Grade 1*	No change in dose	No change in dose

Investigations (Liver Function Tests ALT + AST)	Management/Next Dose for INCB024360	Management/Next Dose for MELITAC 12.1
Grade 2	Off Protocol Therapy	Off Protocol Therapy
Grade 3 or 4	Off Protocol Therapy	Off Protocol Therapy
*For Grade 1 LFT Elevations, increase LFT monitoring to twice weekly.		

Diarrhea	Management/Next Dose for INCB024360	Management/Next Dose for MELITAC 12.1
≤ Grade 1	No change in dose	No change in dose
Grade 2	No change in dose	No change in dose
Grade 3	Off Protocol Therapy	Off Protocol Therapy
Grade 4	Off protocol therapy	Off protocol therapy
Recommended management: physician discretion		

Neutropenia	Management/Next Dose for INCB024360	Management/Next Dose for MELITAC 12.1
≤ Grade 1	No change in dose	No change in dose
Grade 2	No change in dose	No change in dose
Grade 3	Off Protocol Therapy	Off Protocol Therapy
Grade 4	Off protocol therapy	Off protocol therapy
Recommended management: treatment of infection as appropriate		

Thrombocytopenia	Management/Next Dose for INCB024360	Management/Next Dose for MELITAC 12.1
≤ Grade 1	No change in dose	No change in dose
Grade 2	No change in dose	No change in dose
Grade 3	Off protocol therapy	Off protocol therapy
Grade 4	Off protocol therapy	Off protocol therapy
Recommended management: platelet transfusions if indicated		

Fatigue	Management/Next Dose for INCB024360	Management/Next Dose for MELITAC 12.1
≤ Grade 1	No change in dose	No change in dose
Grade 2	No change in dose	No change in dose
Grade 3 or Grade 4	Off Protocol Therapy	Off Protocol Therapy
Recommended management: physician discretion		

Ocular Toxicity	Management/Next Dose for INCB024360	Management/Next Dose for MELITAC 12.1
≤ Grade 1	Off protocol therapy*	Off protocol therapy
Grade 2	Off protocol therapy	Off protocol therapy
Grade 3	Off protocol therapy	Off protocol therapy
Grade 4	Off protocol therapy	Off protocol therapy
*Defined as treatment-related grade 1 ocular toxicities		

Chills/fever/malaise following immunization	Management/Next Dose for INCB024360	Management/Next Dose for MELITAC 12.1
≤ Grade 1	No change in dose	No change in dose
Grade 2	No change in dose	No change in dose
Grade 3	Off protocol therapy if fails to resolve by the next scheduled immunization	Off protocol therapy if fails to resolve by the next scheduled immunization
Grade 4	Off protocol therapy	Off protocol therapy

Injection site reaction	Management/Next Dose for INCB024360	Management/Next Dose for MELITAC 12.1
≤ Grade 1	No change in dose	No change in dose
Grade 2	No change in dose	No change in dose
Grade 3	No change in dose*	No change in dose**
Grade 4	Off protocol therapy	Off protocol therapy

*See section 5.2

** MELITAC 12.1 vaccine may be given if the grade 3 injection site reaction combined area of skin ulceration is <2 cm

